Specific aims are to compare GR antagonism versus placebo for:

1. Changes in resting state FC and CA across key brain regions, focused on nucleus accumbens, amygdala and prefrontal cortex. Hypothesis 1a. GR antagonism will normalize the AUD resting state FC and CA to more closely resemble HC scans. Hypothesis 1b. Magnitude of FC and CA normalization induced by GR antagonism will predict the magnitude of reductions in self-reported CRU alcohol craving and withdrawal in AUD subjects. Hypothesis 1c: The extent of FC and CA dysregulation on day 1 is related to alcohol exposure history.
2. Reduction of alcohol withdrawal symptoms and craving and improvement in low mood during early alcohol abstinence. Hypothesis 2a: GR antagonism will decrease alcohol withdrawal symptoms and craving compared to placebo. Hypothesis 2b: GR antagonism will improve negative mood relative to placebo.
3. Reduction of stress-induced alcohol motivated responding. Hypothesis 3a: Compared to placebo, GR antagonism will decrease alcohol craving and the number of earned drinks following social stress. Hypothesis 3b. The magnitude of FC and CA changes induced by GR antagonism will predict number of drinks earned following stress.
4. Reduction of alcohol sensitivity and reward. Hypothesis 4a: Compared to placebo, GR antagonism will reduce the positive subjective responses and attenuate alcohol-induced increases in heart rate and skin temperature following alcohol administration. Hypothesis 4b: Magnitude of FC and CA changes induced by GR antagonism will predict intensity of self-reported alcohol subjective and physiological effects.
5. Side-effects will be closely monitored in both AUD and HC participants.

3. Background (briefly describe pre-clinical and clinical data, current experience with procedures, drug or device, and any other relevant information to justify the research)

Mechanisms through which cortisol may influence drug related behaviors.

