rs- fMRI analysis. Motion statistics and artifact frequency will be compared to insure that there are no group differences. If necessary, outlier subjects will be removed to achieve equality, or, if this is not possible, motion covariates will be used in analyses. We will determine connectivity using a priori specified seed voxels derived from two sources. The first is from coordinates from previously published studies (Muller-Oehring et al., 2015), or anatomical regions derived from published probability atlases (Hammers et al., 2003; Amunts et al., 2005). Primary regions of interest (ROIs) include ventral striatum/NAcc, mPFC, and central nucleus of the AM (Repunte-Canonigo et al., 2015). Additional seed regions of interest may be identified from group differences observed in the alcohol cue task described below. Connectivity will be measured using the peak cross-correlation between the seed region and other brain regions. These cross correlation results obtained for each subject can then be used in a second-stage analysis for making population inferences and group comparisons. For example, the correlation between the resting-state time series from NAcc and the time series from all other brain regions can be used to create a NAcc correlation volume for each subject. The differences in these correlation volumes before and after drug treatment can be compared for the placebo and drug groups in order to characterize group-dependent differences in altered NAcc connectivity resulting from GR antagonist treatment. We hypothesize that medication groups will exhibit significant differences relative to the AUD placebo group and that fewer differences in connectivity will be observed between HCs and medication groups than between HCs and the AUD placebo group, ie. drug treatments will tend to normalize connectivity toward patterns seen in HCs. In addition to seed-based analyses, we will perform exploratory analyses of whole brain functional connectivity using independent component analyses. Group comparisons will be performed using methods developed and published by our collaborator, [name] (Calhoun et al., 2001; Calhoun et al., 2004). Most recently, [name] and collaborators (Nebel et al., 2015) have used these methods to identify functional connectivity 'signatures' associated with individual differences in symptom severity in children with autism.

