- c. Justification and safety information if non-FDA approved drugs without an IND will be administered.

During the alcohol sensitivity session, subjects will drink 3 doses of alcohol intended to bring their terminal BrAL to 0.10 mg/dL. Also, at the conclusion of the AMR session, participants can consume up to 5 standard drinks of their preferred alcohol type/brand, based on the number of alcohol reinforcers earned during the session. Beverages containing more than 7% alcohol are not regulated by the FDA; they are regulated by the Bureau of Alcohol, Tobacco, Firearms and Explosives. These beverages are legally sold to adults.

7. Study Statistics

- a. Primary outcome variables:

- adverse events and side-effects;

- fMRI changes in re-FC and CA across brain regions under GR regulatory control;
- Reduction in TSST-induced alcohol motivation and drinking;
- cardiovascular responses (HR, BP, ECG) during alcohol sensitivity sessions;
- alcohol euphoric and sedating effects during sensitivity sessions using VAS and Adjective Scales.

b. Secondary outcome variables will examine the effects of MIFE on a variety of psychological measures during alcohol abstinence, alcohol sensitivity sessions and outpatient visits. Secondary outcome measures include:

- Craving for alcohol during the inpatient stay, assessed using VAS, PACS, OCDS, and AUQ;
- Alcohol withdrawal symptom severity, assessed using the CIWA-Ar;
- Mood and personality assessments during the inpatient stay (BPRS, BDI, and BAI);
- Alcohol use during the outpatient follow-up, assessed using timeline followback self-report and PEth levels.

c. Statistical plan including sample size justification and interim data analysis.

Primary and secondary outcome variables will undergo data cleansing and Corrective/Preventive Measures based confirmation of accuracy and missing data. We will perform exploratory data analyses initially (stem-leaf displays, box plots, histograms, and Q-Q plots) and, if necessary, appropriate data transformations will be performed.

Power analyses: All power estimates are based on type I error =0.05, Power > 0.8. Specific aims are to compare GR antagonism versus placebo for:

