Aim 1. Changes in rs-FC and CA across key brain regions under GR gene regulatory control. From the data obtained in preliminary fMRI studies (4.1c), we extracted each subject's connectivity measure (r value converted to Fisher Z score) between left NAcc and 6 mm ROI in the right inferior parietal cortex. Mean and SD connectivity measurement of 0.134, .082 were obtained from alcohol subjects and -.058, .062 were obtained for controls. We made the following assumptions: (a) t1 connectivity will be that of Alc mean (.134) for drug and placebo groups; (b) t2 connectivity will not change for placebo group; (c) t2 connectivity for the drug group will normalize by at least one-third toward HC values, ie: $t2(\text{expt group}) = \text{Alc mean} - (\text{Alc mean} - \text{HC mean})/3 = 0.07$; (d) SD for each cell is the pooled SD (.076); (e) the correlation between repeated measurements (t1 and t2) is 0.5. Using these assumptions a partial eta squared of 0.1563 was calculated for the group x time interaction for a repeated measure ANOVA. Using this estimate with GPower3 (Faul et al., 2007) software we calculated that 25 subjects per group will result in 83% power for detecting a significant interaction at $p < .05$.

Cue-induced Activation: Myrick et al (2008) showed that AUD compared with HC subjects showed increased ventral striatal activation to alcoholic beverage pictures relative to neutral beverage pictures, and that treatment with a combination of naltrexone and ondansetron significantly decreased CA activation. Their paper provided mean and SD information for placebo and drug group ventral striatal activation that was used to estimate effect size for the present proposal for the interaction for a repeated measures anova with between group factor of drug treatment (placebo vs drug) and within group measure of time (baseline and after

treatment). Because this study was performed on a 1.5T scanner, the contrast to noise ratio was multiplied by a factor of 1.3, as described by Hoenig et al.,(2005) to accurately reflect scanning at 3T in the present study. These calculations revealed a partial eta squared value of 0.185, assuming that the drugs in the present study produce at least a comparable effect to the naltrexone/ondansetron treatment. Using this estimate with GPower3 (Faul et al., 2007) software we calculated that 25 subjects per group will result in 90% power for detecting a significant interaction at $p < .05$.

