Aim 1: CA will be measured from contrasts of parameter estimates derived from event-related analysis. FC will be measured using the peak cross-correlation between seed regions and other ROIs. In both cases, results obtained for each subject can then be used in a second-stage analysis for making population inferences and group comparisons (as was done in Fig 6). For example, the correlation between the resting-state time series from NAcc and the time series from all other brain regions can be used to create a NAcc correlation volume for each subject. Using repeated-measure ANCOVA with between-subject factors of drug group (Placebo, GR antagonist) and alcohol history (AUD, HC) and within-subject factors of time (scan 1, scan 2), differences in these correlation volumes before and after drug treatment can be compared for the medication and AUD vs. HC groups in order to characterize group-dependent differences in altered NAcc connectivity resulting from the medication intervention. Potential confounding factors will be examined and added to the model as covariates if necessary. Multi-linear regression will be used to test the correlation between post-treatment FC and CA with the self-reported alcohol craving and withdrawal measures (VAS, OCDS) in AUD subjects. Finally, we test the correlation between FC and CA dysregulation and alcohol exposure history collected from 90-day Time line follow-back (TLFB). Daily alcohol use data collected from TLFB will be summarized as number of drinking days, number of binge drinking days, and number of drinks

per drinking day for all subjects. Then linear regressions models will be constructed to test the correlation between these drinking measures and FC and CA measures from scan 1.

Aim 2: The main outcomes are CIWA-Ar scores for alcohol withdrawal, VAS and OCDS scores for alcohol craving, and Profile of Mood States 2-Short Version subscale scores. The normality of the measures will be examined first and two sample t-test, or equivalent non-parametric methods will be used to compare outcomes between GR antagonist-treated and placebo-treated groups. We will also use ANCOVA model to adjust for potential confounding factors as covariates.

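### Aim 1 does not name the model term that tests Hypothesis 1a, and its power is stated for 25 per group with no HC cell, not for the 50:25 AUD arms

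*Combined protocol and SAP*

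**What the plan says.** Section 2 states Hypothesis 1a: "GR antagonism will normalize the AUD resting state FC and CA to more closely resemble HC scans". Section 7a lists among the primary outcomes "fMRI changes in re-FC and CA across brain regions under GR regulatory control".

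The Aim 1 paragraph of the Statistical Analyses (section 7c) gives the model: "Using repeated-measure ANCOVA with between-subject factors of drug group (Placebo, GR antagonist) and alcohol history (AUD, HC) and within-subject factors of time". Time here means the first and second imaging sessions. The paragraph says before-and-after differences can be compared across medication and AUD/HC groups, and it names no term or contrast as the test of Hypothesis 1a.

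The Aim 1 power paragraph (section 7c) works with two groups. For FC it assumes "t1 connectivity will be that of Alc mean (.134) for drug and placebo groups". The measure is connectivity "between left NAcc and 6 mm ROI in the right inferior parietal cortex", and the result is "25 subjects per group will result in 83% power for detecting a significant interaction". For CA the between-group factor is placebo versus drug, the measure is ventral striatal activation, and the result is 90% at 25 per group.

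Three other places bear on the intended contrast:
- The rs-fMRI analysis text (section 4a) expects that "medication groups will exhibit significant differences relative to the AUD placebo group", and also that medicated groups will differ less from HC than the AUD placebo group does. It adds that "Primary regions of interest (ROIs) include ventral striatum/NAcc, mPFC, and central nucleus of the AM".
- The sentence opening the Statistical Analyses says AUD and HC are grouped separately for Aims 1 to 4.
- The MIFE Administration text sets 2:1 allocation. With 75 AUD subjects (section 5) that is 50:25, the split used in the Aim 4 power statement.

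**The concern.** A model with drug, alcohol history and time offers at least three candidate tests of Hypothesis 1a: drug by time within AUD, drug by time averaged over AUD and HC, and drug by history by time. They answer different questions and have different power. The power paragraph covers only a two-group drug-by-time contrast. That it is AUD-only is explicit for FC, where both groups start at the AUD mean, and inferred for CA, where drug is the only between-group factor.

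Because fMRI change is a primary outcome, leaving the term unnamed allows the choice to be made after the data are seen. The reader also cannot tell which power figure applies.

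**Working it through.** **Inputs.** From the Aim 1 power paragraph, for FC: AUD mean 0.134, HC mean −0.058, one-third normalisation, SD 0.076, scan 1–scan 2 correlation r = 0.5. For CA: partial eta squared 0.185, taken as given because the underlying means are not in the documents. Alpha is 0.05, treated as two-sided. All figures use the noncentral t distribution and are for one uncorrected measure.

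**Step 1: reproduce the plan at 25:25 (df 48).**
- FC: effect = (0.134 + 0.058)/3 = 0.064. SD of change = 0.076 × √(2(1 − 0.5)) = 0.076. So d = 0.064/0.076 = 0.842, and power is 83.1% (plan: 83%).
- CA: t² = 48 × 0.185/0.815 = 10.90. So d = √(10.90 × 2/25) = 0.934 in change-score SD units, and power is 89.9% (plan: 90%).

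The plan's arithmetic is right for its own layout.

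**Step 2: same contrast, actual AUD arms 50:25 (df 73).** SE = √(1/50 + 1/25) = 0.245 SD units. The noncentrality is 0.842/0.245 = 3.44 for FC and 0.934/0.245 = 3.81 for CA. Power is **92.4% FC and 96.4% CA**. With an assumed 10% loss (45:22) it is 89.0% and 94.2%.

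**Step 3: terms that involve HC, at 50/25/50/25 (df 146).** Let k be the HC drug effect divided by the AUD effect. The documents give no value, so k is an assumption.
- Three-way term: effect d(1 − k), SE = √2 × 0.245 = 0.346.
- Averaged drug-by-time term: effect d(1 + k)/2, SE = 0.346/2 = 0.173.

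| k (assumed) | Three-way, FC / CA | Averaged, FC / CA |
|---|---|---|
| −0.5 | 95% / 98% | 23% / 27% |
| 0 | 68% / 76% | 68% / 76% |
| +0.5 | 23% / 27% | 95% / 98% |

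For k between −1 and +1, the three-way term reaches 80% only at k ≤ −0.16 (FC) or ≤ −0.05 (CA). The averaged term does so only at k ≥ +0.16 or ≥ +0.05. Within that range the two never both reach 80%.

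**Step 4: AUD contrast at scan 2 adjusted for scan 1, 50:25 (df 72).**
- FC: d = 0.064/(0.076 × √(1 − r²)). At r = 0.5, d = 0.972 and power is **97.5%**. At r = 0.3 it is 94.5% (change score: 81.8%), and at r = 0.7 it is 99.7% (change score: 99.2%).
- CA, with the effect held fixed on the change scale: d = 0.934/√((1 + r)/2). The plan gives no r for CA. Assuming r = 0.5, d = 1.078 and power is **99.1%**. The range is 99.7% at r = 0.3 to 98.3% at r = 0.7, against 96.4% on change.

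**The case against.** The strongest reply is that the intended contrast is already visible. The power paragraph starts both FC groups at the AUD mean, the rs-fMRI text names the AUD placebo group as comparator, and AUD and HC are to be grouped separately. A within-AUD contrast can also be estimated inside the three-factor model, so a reader who infers that these passages contradict each other goes too far. What remains is that the plan never commits to the contrast. The rs-fMRI sentence is an expectation about connectivity only, and the CA analysis text names no drug contrast.

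A reader might also infer that Aim 1 is underpowered. The documents do not support that. The stated figures are conservative at 50:25, and power falls below 80% only if a term the plan did not power becomes the test and an HC effect is assumed. Nor may one say that no HC effect lets both HC-involving terms reach 80%. With two-sided tests both do once the HC effect is about 2.16 (FC) or 2.05 (CA) times the AUD effect, in either direction. The statement holds only for HC effects no larger than the AUD effect.

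Two further objections stand and shape the remedy. A difference from placebo is not by itself resemblance to HC, so a direction must be stated. Naming a term also leaves the choice of region open unless the measure is named too. Finally, this is a Phase I study seeking preliminary evidence of efficacy, which limits the weight of the point but does not remove it for a listed primary outcome.

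**Conclusion.** The point holds as a specification gap that should be closed. The term that tests Hypothesis 1a is unnamed, and the power is stated for a layout that is not the randomised one. The choice matters: 92% / 96% (FC / CA) for the AUD contrast on change, against 68% / 76% for either HC-involving term if HC show no drug effect. The HC effect is an assumption throughout, as is r = 0.5 for CA. Every figure applies to the single uncorrected measure that was powered, while the rs-fMRI text lists three primary regions. Power for a corrected set of regions would be lower.

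**What to change.** Add to the Aim 1 analysis text: *For FC and for CA, the test of Hypothesis 1a is the MIFE-versus-placebo difference at scan 2 among AUD subjects, adjusted for the subject's scan 1 value and reported with its 95% CI. It counts as normalisation only if the shift is toward the HC mean.* Say which HC scan supplies that mean; scan 1 precedes dosing.

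Name the measure tested for each modality. The powered ones are left NAcc to right inferior parietal cortex for FC and ventral striatum for CA.

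Keep drug by history by time as a supporting analysis, with its power stated as conditional on an assumed HC effect. Also keep as supporting the comparison of each AUD arm with HC from the second half of the rs-fMRI hypothesis.

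Restate power at 50:25 for that single uncorrected measure: FC 92% on change and 97.5% adjusted at the plan's r = 0.5; CA 96% on change and about 99% adjusted if r = 0.5 (98.3% to 99.7% for r from 0.7 to 0.3).

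The change-score test is also valid under randomisation and could be named instead. Adjusting for scan 1 is an efficiency gain from a value already collected. The cost is protocol wording; no subjects, scans or data are added.

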Study Overview: This is a randomized, double-blind inpatient or outpatient human laboratory study. Procedures will be completed as a 7-day inpatient protocol in AUD subjects (N=75) and a 4-day outpatient protocol in an age and gender-matched comparison group of healthy control

(HC) subjects (N=75). On day 1, AUD subjects will be administered an alcohol beverage to control time from last drink before undergoing the first fMRI session. Two hours after alcohol administration, resting-state and alcohol-cued activity will be measured. Following the fMRI session on day 1, all subjects will be randomized to once-daily MIFE or placebo administration. They will also complete cognitive assessment tasks such as the Wisconsin Card Sorting Task (WCST) and two parts of the Wechsler Adult Intelligence Scale-III (WAIS-III), the digit span and the digit symbol substitution tests. They will receive their first medication dose on day 1. Over the next 3 days, AUD participants are monitored as they go through supervised alcohol withdrawal. On day 4, all subjects will complete a second fMRI session to quantify FC changes as a function of alcohol withdrawal and medication administration across key brain regions recently shown to be under GR regulatory control. They will also repeat cognitive assessment tasks. On day 5, AUD subjects complete the Trier Social Stress Test (TSST) followed by the Alcohol Motivated Response (AMR) procedure, during which subjects work for either their preferred alcohol beverage or money. On day 6, AUD subjects will participate in a cumulative alcohol administration procedure during which subjective and physiological responses to alcohol are repeatedly assessed. AUD subjects are discharged on day 7 after completion of the cognitive assessment tasks and a brief intervention. AUD participants are followed for two weeks post discharge. HC participants are followed for one week post second fMRI.

Table 1. Study Day	AUD Procedures	HC Procedures
Pre-admission	Assessment, Medical History, Vital Signs, blood work	Assessment, Medical History, Vital Signs, blood work
Day 1	Updated assessment, blood work, urine pregnancy test; alcohol administration and fMRI session 1 MIFE/placebo randomization and dosing; Cognitive Assessment	Updated assessment, blood work, urine pregnancy test; fMRI session 1 MIFE/placebo randomization and dosing; Cognitive Assessment
CRU stay	Days 2-6: Alcohol withdrawal monitoring	
MIFE/placebo dosing	Days 2-6	Days 2-4

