Daily at 8:00 pm, participants will complete self-reports of alcohol craving, including Visual Analog Scale for alcohol and tobacco craving (VAS); Penn Alcohol Craving Questionnaire (PACS) (Flannery et al., 1999), Beck Depression Inventory-II (BDI-II), Beck Anxiety Inventory (BAI), Obsessive Compulsive Drinking Scale (OCDS), and Alcohol Urge Questionnaire (AUQ). Nursing staff will complete clinician-administered instruments for alcohol withdrawal assessment (see below). Participants will have PRN access to over the counter medications to treat headache, gastrointestinal upset and body aches.

Each day of the CRU stay, the CRU nurse will administer the Systematic Assessment for Treatment of Emergent Events (SAFTEE) (Johnson et al., 2005). This standardized, structured

instrument is specifically adapted for use in substance use disorder clinical trials, to collect information on incidence and severity of medication side effects and adverse events.

To determine if the degree of elevation of CORT in response to GR blockade by MIFE correlates with any of our outcome measures, each morning upon wakening and at bedtime on the CRU, a salivary cortisol sample is obtained. Baseline samples will be collected on day 1, prior to beginning study medications. Measurement of CORT in saliva is not invasive and multiple samples per day are easily obtained. Unlike serum CORT, salivary CORT is unbound to protein and reflects the physiologically relevant fraction. For each sample, subjects chew a pad for 90 sec, which they then place into a capped salivette. Saliva is harvested by centrifugation and stored in a cryotube at -70 until assayed in duplicate (Diagnostic Systems Laboratories; Webster, Texas). The intra- and inter-assay coefficients of variation are below 5%. As we expect variability in CORT within and across MIFE doses, these data will be included in our analyses.

Because MIFE is occasionally associated with hypokalemia, serum potassium level is obtained before study procedures on day 1 and again on day 7 and at the 1 week follow-up visit. Potassium replacement will be addressed as needed.

Outpatient procedures for HC: Healthy control subjects will complete the study as a 4-day outpatient protocol.

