Since MIFE has potent antiprogestational effects, women participants will undergo a urine pregnancy test at the time of the initial alcohol sensitivity and prior to the first MIFE dose. On day 1, participants will be dosed after the fMRI session under nursing observation. On all subsequent days, inpatient participants will be dosed once daily at 9 am under nursing observation and HC outpatient participants will be given take home medication and asked to take the medication under nursing observation via video teleconference. Blood draws for MIFE trough and peak plasma level determinations will be drawn at 15 minutes before dosing and 90 minutes after dosing, respectively. MIFE blood draws will be completed for outpatient HC participants on day 4 only. Subjects can discontinue taking study medication at any time, ending study participation. Discontinued subjects will be asked to complete post-discharge follow up.

fMRI scans for functional connectivity and alcohol cue activation on Days 1 and 4: Both AUD and HC participants undergo fMRI sessions. On day 1, all subjects report to the IPSAR office at 9 am, complete interim assessment procedures, urine drug and pregnancy screens and receive a calorie-controlled breakfast. AUD and HC smokers with tobacco use disorder (TUD) will receive a nicotine patch (21mg). At 10 am on day 1 only, AUD subjects will receive an alcohol drink in a standardized calorie-free mixer targeting a blood alcohol level of 80mg% based on gender and BMI. We have included this drink for several reasons. Most importantly, we want to standardize time from last drink to start of scanning across AUD subjects, since subjects will come for admission with varying abstinence durations. Secondly, we want to minimize the impact of both alcohol intoxication and withdrawal on this initial scan, and so have attempted to time the scan to begin when BAL is at or near 0mg%. Finally, we anticipate that this pre-scan drink will act as a primer for the alcohol cuing procedure employed in the study. At 1 pm, all subjects undergo rs-FC and CA fMRI procedures.

fMRI Scanning procedures: All studies will be conducted at 3T in the F.M.Kirby Research Center for Functional Brain Imaging. We will follow all COVID-related safety procedures implemented by the Kirby Research Center. We will counter-balance for handedness and always use the right hand for responses.

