Aim 2. Reduction of alcohol withdrawal symptoms and craving, and improvement in low mood during early alcohol abstinence. Power for this aim was based on Vendruscolo et al (2015) (Fig 2A) in which MIFE effects were examined on VAS craving scores. Our hypotheses test if placebo (size = n) is different from MIFE. Comparing placebo effects (mean=11.5 (SD=2.1) to active drug effects (mean=9.3 (SD=2.2), total sample size required for the proposed aim is 39 (i.e.,20 in each group).

Aim 3. Reduction of stress-induced alcohol motivation and drinking. Power for this aim was based on Vendruscolo et al (2015) (Fig 2B) in which MIFE effects were examined on drinking during an outpatient treatment phase of the study. This calculation is based on between-subject calculation which overestimates the sample size requirement. Comparing placebo effects (mean (SEM) = 38.0 (10.2)) to active drug effects (mean (SD) = 27.5 (10.2)), total sample size required is 32. Using data from our AMR session in which mean number of drinks is 4.33 (sd = 3.17), we are powered to observe a 50% or greater reduction in drinks earned within the session.

Aim 4. Reduction of alcohol reward and sensitivity. Based on our preliminary data (4A1, Aim 3) and a sample of 50 GR antagonist vs 25 placebo subjects, we are powered to detect a difference of 3.0 degrees (3.3%) in peak skin temperature. Further, using data from our current alcohol sensitivity procedure (mean peak VAS total=168 (SD=118); mean peak liking=47.9 (SD=36.9)), we are powered to observe a 45 - 50% or greater reduction in alcohol subjective effects.

Aim 5. Side-effects. Power calculation is based on the assumption that the number of side-effect reports and adverse events follows a Poisson distribution. In preliminary data (Concept Investigator Brochure), an average of 12 events was reported in MIFE treated subjects. We estimate that 22 subjects in each group will give power > 0.8 for this statistical test.

Statistical Analyses: For aims 1 – 4, AUD and HC subjects will be separately grouped.

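### Hypothesis 1b is about change in FC/CA and in craving, but its regression uses the post-treatment FC/CA level with no scan 1 or treatment-arm term, so a significant result need not support it

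*Combined protocol and SAP*

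**What the plan says.** For the AUD group, Section 2 words Hypothesis 1b as follows: "Magnitude of FC and CA normalization induced by GR antagonism will predict the magnitude of reductions in self-reported CRU alcohol craving and withdrawal". Both sides of that statement are changes. Hypotheses 3b and 4b also take the magnitude of FC/CA change as the predictor.

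Section 7c, Statistical Analyses, Aim 1, gives the only regression that matches 1b, limited to the AUD group: "Multi-linear regression will be used to test the correlation between post-treatment FC and CA with the self-reported alcohol craving and withdrawal measures (VAS, OCDS". Time (scan 1, scan 2) and drug group are named in the repeated-measures ANCOVA for the group comparison, and scan 1 in the regression on drinking history. Neither is named here. The sentence just before it says: "Potential confounding factors will be examined and added to the model as covariates if necessary". Section 7c names no regression for 3b or 4b.

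On timing, Section 4a, General CRU procedures, has: "Daily at 8:00 pm, participants will complete self-reports of alcohol craving". MIFE Administration adds: "On day 1, participants will be dosed after the fMRI session under nursing observation". The day 1 scan is at 1 pm, so the first scheduled VAS/OCDS comes after the first dose. Sections 7b and 7c treat VAS and OCDS as craving measures and CIWA-Ar as the withdrawal measure.

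**The concern.** A post-treatment level is not a change. A subject can have a low scan 2 value because the drug lowered it or because it was already low at scan 1. Without scan 1 the regression cannot tell these apart. Without arm, a drug that shifts both FC and craving produces a correlation between them even if, within each arm, subjects with more FC change have no more craving change. Either route could be reported as support for 1b.

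Three further gaps sit in the same sentence. The outcome is not stated as a reduction. No starting craving score is named. No withdrawal measure is named, although 1b includes withdrawal.

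At stake is the mechanistic claim that brain normalization tracks clinical improvement.

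**Working it through.** **Inputs from the plan**
- Section 7c, Power, Aim 1: FC mean 0.134 in AUD, -0.058 in controls, one-third normalization, SD 0.076 per cell, and "the correlation between repeated measurements (t1 and t2) is 0.5".
- Section 7c, Power, Aim 2: "Comparing placebo effects (mean=11.5 (SD=2.1) to active drug effects (mean=9.3 (SD=2.2".
- Section 7c, Power, Aim 4: 50 drug and 25 placebo AUD subjects.
- Alpha 0.05, taken as two-sided.

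**The plan's own figure.** Drug effect on FC = 0.192/3 = 0.064. SD of change = 0.076 × √(2 × (1 − 0.5)) = 0.076. d = 0.064/0.076 = 0.842. With 25 per group, the noncentral t gives 83.1% against the stated 83%. That figure is for the group-by-time test and is not in dispute. The plan gives no power for 1b.

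**Level against change.** With equal SDs, |corr(post, change)| = √((1 − ρ)/2) = √(0.5/2) = 0.50 at ρ = 0.5, so they share 25% of their variance.

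**False support 1: arm effects only.** Craving effect = (11.5 − 9.3)/√((2.1² + 2.2²)/2) = 2.2/2.15 = 1.02 SD. Arm variance = (50/75)(25/75) = 2/9. Correlation created by arm alone = (2/9)(0.842)(1.02)/√[(1 + (2/9)0.842²)(1 + (2/9)1.02²)] = 0.160. Fisher z with n = 75: atanh(0.160) × √72 = 1.37, so it is significant in about 28% of trials.

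**False support 2: craving follows only scan 1 FC.** If craving correlates s with scan 1 FC within arm, it correlates 0.5s with scan 2 FC. For s = 0.3 or 0.5 (assumed) this is 0.15 or 0.25. Fisher z gives 25% or 58%; simulation gives about 25% or 57%.

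**Simulation.** Ordinary least squares, FC and craving standardized, starting and later craving correlated 0.5 (assumed). Rates are good to about one point.

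| Situation with no true link | Model | Significant |
|---|---|---|
| Arm effects only | post alone | 28% |
| Arm effects only | change score alone | 29% |
| Arm effects only | post + scan 1 | 34% |
| Arm effects only | post + scan 1 + arm | 5% |
| Scan 1 drives craving, 0.3 / 0.5 | post + arm | 25 / 57% |
| Scan 1 drives craving, 0.3 / 0.5 | change score + arm + starting craving | 31 / 71% |
| Scan 1 drives craving, 0.3 / 0.5 | post + scan 1 + arm | 5 / 5% |

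Both terms are needed, and a bare change score does not replace them.

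**Power when a link exists** (assumed strength 0.3 / 0.4 / 0.5, every model with arm):

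| Mechanism | post | + scan 1 | + scan 1 + starting craving |
|---|---|---|---|
| Later craving depends on FC change | 25 / 41 / 58% | 62 / 87 / 98% | 75 / 96 / 99.8% |
| Craving tracks FC at the same time | 74 / 95 / 99.7% | 62 / 87 / 98% | 73 / 94 / 99.6% |

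Under the first mechanism the stated predictor loses much power. Under the second it loses none, and adding scan 1 without a starting score costs some.

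**Limits of the adjusted model.** If the drug does not shift FC at all but FC change drives craving in both arms, the pooled slope is still significant in 75 / 96 / 99.8%, and the arm interaction in 5%. If the link exists only under MIFE, the MIFE-arm slope has 57 / 84 / 97% power and the interaction 23 / 38 / 57%.

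**The case against.** The text is silent rather than wrong: a multi-linear model has several predictors, and the preceding sentence allows confounders. It is true that nothing forbids scan 1 or arm. But that sentence is conditional, follows the ANCOVA and commits to neither term. These two terms define the quantity in 1b, so they should not wait on a look at the data.

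The power loss depends on an assumed mechanism. This stands in full. If craving tracks concurrent FC, the adjusted model gains nothing.

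The adjusted slope can also mislead. This stands too: it can be significant with no drug shift in FC, and scan 2 is itself meant to "quantify FC changes as a function of alcohol withdrawal and medication administration across key brain regions". The slope must be read with the ANCOVA result.

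A regression without a healthy-control reference does not test normalization as such. This stands and is taken up in the fix.

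The inputs are narrow. The FC figures come from one accumbens-parietal pair, parietal cortex is not among the primary regions, and no CA inputs were used. The rates are therefore illustrations, but the mismatch does not depend on them.

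Hypothesis 1b is also neither a listed primary nor secondary outcome. That limits the weight of the point but does not remove it, since the hypothesis is stated and a test is planned for it.

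**Conclusion.** The planned regression does not test Hypothesis 1b as stated. Read literally, it can credit 1b to an arm effect (about 28%) or, with arm added, to pre-drug FC (about 25% or 57%). With scan 1 and arm both in the model each rate is about 5%. The case for change is validity for 1b, not an assured gain in power.

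Three stronger readings are tempting and are not supported:
- A reader might infer that the analysis is underpowered for 1b. The documents give neither a power target nor a mechanism, and under a concurrent link the stated predictor does as well as the full model.
- A reader might infer that scan 1 and arm are excluded. They are unnamed, not ruled out.
- A reader might infer that the Aim 1 treatment comparison is flawed. Its ANCOVA names time and drug group, and its 83% reproduces.

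The figures rest on ρ = 0.5 and the arm effects from the plan, on assumed link strengths, and on usable paired scans in all 75 AUD subjects. At about 67 (roughly 90% of 75), full-model power under the change mechanism falls from 75 / 96 / 99.8% to 69 / 93 / 99.6%. The point should be corrected, but it concerns the mechanistic hypotheses only; the treatment-effect ANCOVA and the listed primary and secondary outcomes are untouched.

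**What to change.** In Section 7c, Aim 1, state for AUD subjects:
- Outcome: a named later VAS/OCDS score, for example day 4 at 8 pm, the last rating before the day 5 drinks.
- Predictor: scan 2 FC/CA, with scan 1 FC/CA, treatment arm and a named starting craving score in the model.
- Which direction of change counts as normalization, relative to the healthy-control scan values.
- Also reported: the MIFE-arm slope and the arm interaction (scan 2 × arm, with scan 1 × arm). The result is associational and is read beside the ANCOVA effect on FC/CA.
- A withdrawal measure, or withdrawal dropped from this test. CIWA-Ar is collected but nurse-completed, so the self-report wording would need to change.

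Use the same scan 1- and arm-adjusted predictor for Hypotheses 3b and 4b.

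State the limits of the timing. The day 1 8 pm score follows the first dose, the 10 am alcohol drink, and the spirits sip and cues at scan 1; adjusting for it may remove part of an early drug effect. The day 4 8 pm score follows scan 2 and its cues.

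Cost: wording only if the day 1 8 pm score is used. A pre-scan, pre-dose VAS/OCDS on day 1 would avoid the day 1 problem for one extra rating. Downsides: some power is lost if craving tracks concurrent FC and no starting score is used. Some is also lost against a change score if craving truly follows change (at 0.4, 87% against 95% without a starting score, 96% against 99% with one). Power for the interaction is low.
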